The exclusion criteria are: 1) pregnant or breastfeeding women; 2) abdominal pain lasting >96 hours before admission; 3) the possibility of poor oral intake for reasons other than AP; 4) Pancreatic neoplasm, endoscopic retrograde cholangiopancreatography or trauma etiology; 5) Chronic pancreatitis; 6) Randomization greater than 12 hours after admission.

Sample size

Given that historically the duration of hospitalization for mild AP at two hospitals is 7 days, a sample size of 120 patients (60 in each group) will be necessary to be recruited using a 10% drop-out rate, 80% power and 95% significance level to detect a two-day difference in total length of hospital stay between the study groups.

Randomisation

In each centre participants will be divided into two groups receiving one of the two study treatments. The allocation of participants to the different groups will be carried out based of predefined randomization lists created separately for each recruiting centre. The randomization lists will be prepared with a block size of 2 and with an allocation ratio of 1:1.

Duration

The planned starting date of the study is June 1st, 2017 and the planned finishing date of the study is December 31st, 2018.

Intervention

Based on the currently available guidelines, oral refeeding can be started early for patients with mild and moderate AP. Additionally, with an LFSD appeared safe and provided more calories. Therefore, both groups can be regarded as being treated within accepted practice recommendations. In this study, EORF with LFSD will be the intervention. Patients will be randomized to group A or PADI diet (EORF with LFSD) or fasting group.

Groups

In group A (PADI), the oral refeeding will be started after admission. Patients will receive a low fat solid diet with more and less 1500 calories, 35 g fat day.

In group B (fasting), the oral diet will be reintroduced in a traditional stepwise manner until the symptoms, signs, inflammatory parameters of AP have resolved.

General patient management

General treatment intimated by the IAP / APA guideline will be used.

All patients will receive adequate intravenous fluid resuscitation based on their individual hemodynamic parameters and fluid balanced. The patients will be monitored daily for gastrointestinal symptoms, abdominal pain, total intake/output, nutritional parameters, and laboratory findings.

Endpoints

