The primary endpoint is length of hospitalization. Several secondary endpoints such as pain, the duration of fasting, tolerance to food, relapse rate, degree of transitional abdominal distension and/or abdominal pain and/or vomits after the first ingestion of oral food, multiorgan failure, pancreatic infection, hyperglycemia, nutritional parameters, mortality and quality of life will be determined to elucidate more detailed differences between the groups. The feasibility, safety and quality checks required for high quality evidence will be adhered.

Monitored parameters during hospitalisation

There will be a large variety of parameters monitored during the study: medical history, physical examination, laboratory test, diagnostic imaging, therapy, complications, interventions. The data collection will be done in the form A. This form will contain parameters collected on admission, parameters every day during hospital admission and contain parameters 1 month after hospital discharge.

Data management and statistical analyses

The investigator will ensure that the data in the form A are accurate, complete and legible. Detailed data flow will be described in a Data Management Plan. Data from completed form A will be validated under direction of the Data Manager according to a Data Cleaning

Plan. Any missing, or inconsistent recordings in the form A will be referred back to the investigator of each centre. The Data manager is a biostatistician.

Study populations

Three analysis populations will be defined:

Safety Analysis Set (SAS): all patients enrolled in the study.

Per Protocol Set (PPS): all enrolled patients who finished the study conforming to the requirements of the study protocol.

Intention to Treat (ITT): all randomized participants who start on a treatment, excluding consent withdrawals.

Withdrawal of a subject from Per Protocol Set

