Any participants / investigators and Data manager can submit recommendations for dropouts from the PPS group with reasons given to the coordinator. The coordinator will discuss all the recommendations all the information and, if the alteration in the protocol would be expected to have any bearing on the interventions and outcomes of the study, the patient will not be included in the final pre-protocol analysis. Automatic dropout from per-protocol group shall be ordered if: 1) any of the exclusion criteria are diagnosed during the course of AP; 2) parameters for answering the primary endpoints are missed; or 3) serious medical reasons nor related to pancreatitis occur.

Applied software

Statistical analysis will be performed using SPSS 21 statistical packages. Pages Mac will be used for reporting.

Statistical methods

Baseline patient and disease characteristics will be analyzed using descriptive analysis. Demographic and baseline characteristics will be summarized for the overall study population. Continuous variables will be described by mean, median, SD and ranges and categorical variables will be described by absolute and relative frequencies. A graphical presentation of efficacy variables will be prepared. Descriptive statistics for both the primary and secondary parameters will be analyzed similarly. Mean changes (with 95% CI) from baseline to end-of-study visit will be presented. Chi-square test will be applied to compare proportions between the different groups. Survivals will be investigated using the Kaplan-Meier analysis method, while subgroup comparisons will be performed using the Chi-square or Fisher's exact test, as appropriate. For safety data, descriptive statistics and individual listing of adverse events will also be presented.

Centres

The trial will start in six centres:

1. Consorci Sanitari del Garraf - Hospital Residencia San Camil
2. Hospital Universitari Joan XXIII de Tarragona
3. Hospital Clinic de Barcelona

In all centre the coordinator will make an audit of the centre and will report to Data Manager.

Publication policy

Centres providing more than 20 patients can provide one authors to the authorship list. Every additional 20 patients will give the opportunity to nominate an additional author.

Feasibility and safety

The diet is a general protocol for the treatment of AP.

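### The only interval estimate stated for continuous secondary endpoints is an unadjusted change from baseline; a comparison adjusted for the admission value would be at least as precise, by a margin the documents do not fix.

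*Combined protocol and SAP*

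**What the plan says.** The Statistical methods section says "Descriptive statistics for both the primary and secondary parameters will be analyzed similarly", and the next sentence is "Mean changes (with 95% CI) from baseline to end-of-study visit will be presented". No other confidence interval is mentioned for a continuous outcome. The comparison it names is for proportions ("Chi-square test will be applied to compare proportions between the different groups"), with Fisher's exact test as an alternative for subgroups and Kaplan-Meier for survival. No regression, covariance analysis or other use of a baseline value as a covariate appears anywhere.

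The Endpoints section lists "Several secondary endpoints such as pain, the duration of fasting, tolerance to food, relapse rate" and, later in the same sentence, "hyperglycemia, nutritional parameters, mortality and quality of life will be determined". It gives their purpose as showing differences between the groups. The primary endpoint is separate: "The primary endpoint is length of hospitalization".

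On timing, the section on monitored parameters says of form A: "This form will contain parameters collected on admission, parameters every day during hospital admission and contain parameters 1 month after hospital discharge". The exclusion criteria include "Randomization greater than 12 hours after admission". Neither baseline nor end-of-study visit is defined. The natural reading is admission and 1 month after discharge.

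**The concern.** On the natural reading, baseline is taken during the acute attack and the end-of-study value in recovery. Two such values may be only weakly correlated. For pain, the admission value may also be the more variable, since recovered patients may cluster near zero. In either case a change score carries the variation of the admission value into the result without removing much variation from the follow-up value. It also over-corrects a chance baseline imbalance whenever the regression slope of follow-up on admission is below 1.

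At stake is the precision of a few secondary comparisons in a trial with at most 60 patients per arm. Intervals could be wider than the collected data require. In addition, if the between-arm estimator is not fixed in advance, the choice between change, follow-up value and adjusted value could be made after the results are seen.

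**Working it through.** **Inputs from the documents.** 120 patients, 60 per arm, 1:1 allocation, 10% dropout (Sample size, Randomisation). Evaluable per arm: 60 × 0.9 = 54. The stated 95% significance level is read as two-sided alpha 0.05; sidedness is not given.

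**The plan's own figure.** The 120 is for length of stay, and no SD is stated, so it cannot be reproduced independently. It is consistent with an SD of about 3.7 days: a two-day difference at 80% power then needs 54 per arm, and 54/0.9 = 60. This has no bearing on the present point, because length of stay has no baseline value. The documents state no precision for any continuous secondary endpoint.

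**Assumptions.** r, the correlation between admission and follow-up values; k, admission SD divided by follow-up SD; and a true difference of 0.5 follow-up SD. None is in the documents, so a range is shown. Power comes from the noncentral t distribution and so assumes roughly normal data.

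**Formulas.** Variance per patient, with follow-up SD set to 1:
- change from baseline: 1 + k² − 2rk
- follow-up value alone: 1
- adjusted for the admission value: 1 − r²

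Change minus adjusted is (1 + k² − 2rk) − (1 − r²) = (k − r)². This is never negative and is zero only when r = k. Change is noisier than follow-up alone when k² − 2rk > 0, that is, when r < k/2. At equal SDs the threshold is r = 0.5.

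**Worked case, k = 1, r = 0.3.** Change: 1 + 1 − 0.6 = 1.40. Adjusted: 1 − 0.09 = 0.91. Ratio: 0.91/1.40 = 0.65. The adjusted interval is narrower by 1 − √0.65 = 19.4%. Change scores on 54 per arm give the precision of the adjusted analysis on 54 × 0.65 ≈ 35 per arm.

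| k | r | Var. change | Var. adjusted | Adjusted/change | Power, change | Power, follow-up alone | Power, adjusted |
|---|---|---|---|---|---|---|---|
| 1 | 0.3 | 1.40 | 0.91 | 0.65 | 58.5% | 73.1% | 77.0% |
| 1.5 | 0.3 | 2.35 | 0.91 | 0.39 | 39.0% | 73.1% | 77.0% |
| 2 | 0.3 | 3.80 | 0.91 | 0.24 | 26.2% | 73.1% | 77.0% |
| 1 | 0.7 | 0.60 | 0.51 | 0.85 | 91.4% | 73.1% | 95.0% |
| 0.75 | 0.7 | 0.5125 | 0.51 | 0.995 | 94.9% | 73.1% | 95.0% |

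Simulation with 10,000 runs per setting gave adjusted/change ratios of 0.66 (k=1, r=0.3), 0.75 (k=1, r=0.5), 0.91 (k=1, r=0.8) and 0.38 (k=1.5, r=0.3). The formulas give 0.65, 0.75, 0.90 and 0.39.

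**Which endpoints are reached.** Pain and nutritional parameters can have both an admission and a later value. So can quality of life, but the documents do not say that it is recorded at admission. Duration of fasting has no baseline, and most of the rest of the list are events.

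**The case against.** The strongest objection is that the sentence is descriptive. It follows a sentence on descriptive statistics, says only that changes will be presented, and names no test or between-arm contrast on change. The interval may be for the change within each arm. This stands: a reader might infer that the plan has chosen raw change as its between-arm estimator, and the text does not say so. The point is therefore conditional on arms being compared on those changes. It does not vanish, because on the descriptive reading these endpoints have no stated between-arm estimate at all, although they are meant to show group differences. One added sentence settles both readings.

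Second, the same section describes continuous variables by mean, median, SD and range, so follow-up values would be reported too. This also stands. In the first three rows of the table, a plain comparison of follow-up values recovers most of the power: 73.1% against 77.0%.

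Third, a reader might infer that subtracting the admission value adds noise here, and that adjustment would be markedly better. The documents do not support either as fact. At k=1, r=0.7 subtraction removes noise (variance 0.60 of follow-up alone), and at k=0.75, r=0.7 adjustment gains almost nothing. The size also depends on the visit chosen, because daily and 1-month values need not correlate equally with admission.

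Fourth, it does not follow that real differences will probably be missed. Power below one half for change scores arises in the table only with k of 1.5 or 2, and the 0.5 SD effect is itself assumed. Finally, in randomised arms change scores are unbiased on average, so over-correction concerns chance imbalance only.

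**Conclusion.** The point holds as a low-cost improvement for a small group of secondary endpoints, not as an error that threatens the trial. What the documents establish is that unadjusted change from baseline is the only interval estimate stated for continuous outcomes, and that no baseline-adjusted comparison is planned. What the algebra establishes is that, if arms are compared on change, adjustment for the admission value is at least as precise in large samples, at a cost of one degree of freedom.

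The size of the gain is open. Over the assumed values shown, it runs from more than 50 percentage points of power (k=2, r=0.3) to nothing of consequence (k=0.75, r=0.7). Low correlation or a more variable admission value is plausible for a measurement taken in the acute phase, but nothing in the documents shows it. The length-of-stay analysis and the 120-patient target are untouched.

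**What to change.** In Statistical methods, replace the sentence on mean changes with:

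*For each continuous secondary endpoint recorded on admission, the between-arm difference (A minus B, 95% CI) at the end-of-study visit (1 month after discharge, or for in-hospital measures one named hospital day) will be estimated by linear regression on arm and the admission value of the same variable; mean changes are shown descriptively only.*

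The follow-up time must be named for each endpoint; otherwise the choice among daily and 1-month values stays open. A hospital day should be early enough that most patients in both arms are still in hospital, since the intervention is expected to shorten the stay. The plan should also define baseline as the admission value, state whether quality of life is recorded then, and give the pain scale, so that the suitability of a linear model can be judged.

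The cost is this sentence, those definitions and a standard general linear model in SPSS, the package already named. No new visits or patients are needed. Form A already has an admission section, so no new data are needed for any variable recorded there.

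### First-meal symptoms are an endpoint worded as a degree, but the plan gives no scale and names no test that uses the order of grades

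*Combined protocol and SAP*

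**What the plan says.** The Endpoints section lists among the secondary endpoints the "degree of transitional abdominal distension and/or abdominal pain and/or vomits after the first ingestion of oral food". It gives no scale, number of grades or cut-off, and does not say whether the three symptoms are graded separately or together. Data are to be collected on form A, which is not part of the documents.

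Under Statistical methods, "categorical variables will be described by absolute and relative frequencies". For comparisons between groups the section says "Chi-square test will be applied to compare proportions between the different groups". It adds that "subgroup comparisons will be performed using the Chi-square or Fisher's exact test, as appropriate". The rest is descriptive summaries, mean changes from baseline with confidence intervals, and Kaplan-Meier. No rank, trend or ordinal method is named for any endpoint, and no test is tied to any particular endpoint.

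The Sample size section covers length of stay only. It says that "a sample size of 120 patients (60 in each group) will be necessary to be recruited". The inputs it gives are drop-out of 10%, power of 80% and a significance level written as 95%.

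**The concern.** A degree of symptoms is naturally an ordered measure. If the named tests are applied to it, only two comparisons are open. One is a chi-square on the full table of grades, which treats the grades as unordered labels. The other is a chi-square on a proportion such as any symptom versus none, which counts mild distension and severe pain as the same result. A change-from-baseline summary does not help, because symptoms after the first meal have no pre-meal value of the same kind.

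The Discussion section's main hypothesis has two parts, that early feeding is well tolerated and that it shortens the stay. First-meal symptoms bear on the first part. With 60 per arm before drop-out, a test that discards order or grade makes a real shift in severity easier to miss. Leaving scale, cut-point and test open also means that they could be settled after the data have been seen.

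**Working it through.** **1. The plan's own figure.** The only stated sample size is 120, for length of stay. It cannot be reproduced, because no standard deviation is given. The usual formula is n per arm = 2 × (1.96 + 0.84)² × SD² / 2². An SD of about 3.7 days gives 2 × 7.85 × 13.69 / 4 = 53.7, so 54, and 54 / 0.9 = 60 per arm. This does not bear on the first-meal endpoint, for which the plan states no power. It only supports the evaluable number used below: 60 × (1 − 0.10) = 54 per arm.

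**2. Assumed inputs.** The documents give no grades, rates or effect for this endpoint. The following are assumptions:
- two-sided 5%, because sidedness is not stated;
- four ordered grades, with a symptom-free share in the reference arm between 25% and 80%, or three grades (50/30/20%, 70/20/10% or 80/15/5%);
- a proportional-odds shift with common odds ratio (OR) 1.5, 2, 2.5 or 3, towards worse or towards fewer symptoms.

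**3. How the shift works.** With reference grades 50/25/15/10%, the cumulative proportions are 50, 75 and 90%, so the cumulative odds are 1, 3 and 9. For worsening at OR 2.5, divide by 2.5 to get 0.4, 1.2 and 3.6. Converting back by odds / (1 + odds) gives 28.6, 54.5 and 78.3%, so the grades are 28.6/26.0/23.7/21.7%. For fewer symptoms, multiply by 2.5 instead.

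**4. Tests compared.** There were 20,000 simulated trials per scenario. Three tests were compared: Wilcoxon-Mann-Whitney with tie correction; Pearson chi-square, Σ(O − E)²/E, on the full table (3 degrees of freedom for four grades, 2 for three); and 2×2 chi-square on any versus none. At OR 1 all three rejected in about 4% to 5.5% of trials.

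**5. Worked examples, 54 per arm.**

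| Reference grades, OR, direction | Rank test | Unordered chi-square | Any versus none |
|---|---|---|---|
| 50/25/15/10%, 2.5, worse | 74% | 57% | 63% |
| 50/25/15/10%, 2.5, fewer | 66% | 48% | 63% |
| 70/20/10%, 2, fewer | 33% | 25% | 33% |

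The gains over the unordered table are 74 − 57 = 17, 66 − 48 = 18 and 33 − 25 = 8 points. Over any versus none they are 11, 3 and 0 points.

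**6. Range over the scenarios.**

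| Rank test compared with | OR | Gain in power (points) |
|---|---|---|
| Unordered chi-square, 4 grades | 2 to 3 | about 12 to 21 |
| Unordered chi-square, 3 grades | 2 to 3 | about 7 to 12 |
| Unordered chi-square, 4 grades | 1.5 | about 5 to 8 |
| Unordered chi-square, 3 grades (50/30/20 or 70/20/10%) | 1.5 | about 4 to 5 |
| Any versus none, 4 grades, shift to worse | 2 to 3 | about 1 to 32 |
| Any versus none, shift to fewer | 1.5 to 3 | about 0 to 13 |

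The gain over any versus none is under 5 points when 70% or more of the reference arm are symptom-free. It is about 0 to 3 points when half or more are symptom-free and the shift is towards fewer symptoms. Apart from simulation error, the rank test was never worse than either chi-square option.

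**The case against.** The strongest objection is that the plan never says chi-square will be used for this endpoint. A reader might infer that it does, but the sentence concerns proportions in general. No between-group test is named for continuous outcomes either, not even for length of stay. The gap is therefore an omission, not a stated wrong choice. This stands, and the point is worded accordingly.

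The ordered scale is also inferred from one word. Form A might record grades, a numeric score, a symptom count or only yes/no, and vomiting could well be binary. This stands too: the scale must be stated before any test can be named, and it cannot be promised that the needed grades are already collected.

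A reader might also take one figure, such as 12 to 18 points, as the loss built into the plan. The documents do not support that. Such a range needs four grades, an odds ratio of 2 to 3, a shift towards worse symptoms and an unordered table. Changing any of these moves the figure, and against any versus none it can vanish.

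Finally, this is one of eleven secondary endpoints, it has no power claim, and tolerance to food is listed separately. That limits the importance of the point. It does not remove the mismatch between an endpoint worded as a degree and a section with no method that uses order.

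**Conclusion.** The concern holds in limited form. The endpoint is worded as an ordered severity measure, its scale is undefined, and neither chi-square nor Fisher's exact test uses order. The gain from a rank test is a conditional range. It is about 12 to 21 points over an unordered four-grade table and 7 to 12 over a three-grade table at odds ratios of 2 to 3, about 4 to 8 at 1.5, and about 0 to 32 over any versus none. These figures rest on 54 evaluable per arm, assumed grade distributions and a shift of similar size at every cut-point. A treatment effect that raised some grades and lowered others in no consistent direction would not favour the rank test.

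It should not be inferred that the sample size of 120 is wrong on this account. That figure was set "to detect a two-day difference in total length of hospital stay between the study groups", and the first-meal endpoint plays no part in it. The change is worth making, but it concerns a secondary endpoint only.

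**What to change.** First, state in the Endpoints section the ordered grades that form A records for this endpoint, and whether distension, pain and vomiting are graded separately or as one measure. Then add to Statistical methods:

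*The degree of symptoms after the first oral food will be compared between groups on its full ordered scale by the Wilcoxon-Mann-Whitney test, with a proportional-odds common odds ratio and 95% CI; the proportion with any symptom will be reported descriptively.*

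If the three symptoms are graded separately, label the three comparisons as secondary and unadjusted for multiplicity. Keep chi-square or Fisher's exact test for any component recorded only as yes/no and for the other binary outcomes.

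The cost is a sentence or two of text and no extra patients or visits. If form A does not yet record grades, it also needs an added item. An odds ratio is less intuitive than a difference in percentages, which is why the any-symptom percentages are kept.
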